3.2 Second study (visit 3, for EAA/protein Arm)

After approximate minimum 1-week washout period, subjects who enrolled into the EAA/protein arm will undergo a second stable isotope study as described above. The order of consumption of each beverage will be randomized. The opposite leg will be used for muscle protein synthesis measurements. No further DEXA will be performed.

3.3 Subject Compensation

Subjects will accrue compensation for every visit according to the below table. They will be mailed a check for their total compensation approximately 2-3 weeks after their participation ceases (whether completed or not). If they were to attend every visit, their total amount would be \$325 for the whey arm and \$625 for the EAA/protein arm. If they stop participating during a stable isotope study visit, they will receive prorated pay of \$25 per hour.

Visit	Amount
1	\$25
2	up to \$300
3 (if applicable)	up to \$300

3.4 Randomization for EAA/protein Arm

Study staff will strive to maintain gender balance between the two arms. A randomization list will be implemented to reveal which dosage of EAA/protein will be tested first in the case of the cross-over study (Arm 1).

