3.0 Study Design and Procedures

We will study a total of up to 20 healthy male and females between 18 and 50 years of age. We will use a randomized, two-period, stable isotope (Cambridge Isotope Labs, Tewksbury, Mass.) infusion study: 4.5-hour basal fasted period and 4-hour post-meal period (total 8.5-h time period). The principal end-point will be the total anabolic response (whole body protein synthesis minus breakdown) and the secondary end point will be muscle protein fractional synthetic rate (FSR) over the 4 hours following the consumption of either the test composition or whey protein. The plasma amino acid response will also be a secondary end point.

We will utilize two distinct arms within this protocol. Arm 1 will consist of a group of subjects who will perform a randomized, single blind cross-over (two stable isotope studies) between the two doses of the EAA/protein study supplement, with a \geq oneweek washout period between stable isotope studies. Arm 2 will consist of a group of subjects (with similar gender composition) who will undergo one stable isotope study during which they will ingest the whey protein isolate study supplement. Subjects will be enrolled into the double stable isotope study arm, utilizing the specific consent form. After Arm 1 enrollment is completed, unique future subjects will be enrolled into Arm 2 – the single stable isotope arm, using the specific consent form.

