7.0 Data Analysis

7.1 Statistical Analysis plan

The purpose of this study is to estimate and compare the effect of two different nutritional beverages on total anabolic response (TAR) and muscle protein synthesis (MPS). To this end, an analysis of covariance (ANCOVA) model will be employed to compare the protein sources with respect to mean response (either TAR or MPS) after adjusting for basal measures. If a significant protein group effect is detected, then pairwise comparisons will be performed to determine if the two sources or two doses differ. In this case, the Tukey-Kramer method will be used to adjust for multiple comparisons. A 5% will be used to determine statistical significance.

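### Sex is to be kept similar between the product and whey arms but is not in the ANCOVA; prespecifying it is a cheap improvement if sex predicts the response beyond the basal measure.

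*Combined protocol and SAP*

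**What the plan says.** Section 3.0 (Study Design and Procedures) sets up two separate groups. Arm 1 crosses over between two doses of the product. For whey, "Arm 2 will consist of a group of subjects (with similar gender composition) who will undergo one stable isotope study". Recruitment is sequential: "After Arm 1 enrollment is completed, unique future subjects will be enrolled into Arm 2". Under Section 3.4 only the dose order within Arm 1 is randomised. The same section adds that "Study staff will strive to maintain gender balance between the two arms". Neither section gives a ratio, a quota or a matching rule.

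In Section 7.1, "an analysis of covariance (ANCOVA) model will be employed to compare the protein sources with respect to mean response", for TAR and for MPS, "after adjusting for basal measures". If the group effect is significant, pairwise comparisons follow, and "the Tukey-Kramer method will be used to adjust for multiple comparisons". Neither sex nor a subject effect is named as a model term. Section 7.2 plans 8 subjects per arm and assumes that the basal covariate explains 50% of the variation. No section gives the size of a sex effect on either outcome.

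**The concern.** Superiority over whey is half of the hypothesis in Section 2.0. It rests on 8 against 8 subjects who are not randomised to arm, so only the recruitment aim protects sex balance.

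If sex predicts the response after basal adjustment, leaving it out has two possible consequences:

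- **Balance achieved.** The sex difference cancels from the arm contrast but stays in the residual. The standard error is then too large and power is lost.
- **Balance missed.** Part of the sex difference enters the estimate of product minus whey.

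A sex term deals with both. Under Section 3.5 the data analyst knows which product was taken, so the term is better fixed in advance than chosen after the data are seen.

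**Working it through.** **1. The plan's own figure.** Section 7.2 gives 80% power at f = 0.484 with a basal R² of 50%. For a one-way ANCOVA with k = 3 groups, N = 24 observations (8 × 3 beverage conditions) and one covariate, the degrees of freedom are 2 and 24 − 3 − 1 = 20. The noncentrality is λ = N f²/(1 − R²) = 24 × 0.484²/0.5 = 11.24, which gives power 0.8003. All five rows of Table 1 reproduce within 0.001. The planned model therefore counts 24 observations with no subject term.

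**2. Assumption.** Let r be the share of the post-basal variance that sex explains, with r from 0 to 0.30. Residual SD means the SD after basal adjustment, sex included. With equal numbers of women and men, the sex difference is 2√r residual SD.

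**3. Balance achieved (4/4 against 4/4).** With 16 subjects, two arm means and one basal slope, 13 residual df remain. Without sex in the model, the expected residual mean square is proportional to [13(1 − r) + 16r]/13, while the contrast's true variance is proportional to 1 − r. The overstatement of the standard error is √{[13(1 − r) + 16r]/[13(1 − r)]}. At r = 0.10 this is √(13.3/11.7) = 1.066, or 7%.

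Adding sex leaves 12 df, so the interval width changes by (2.179/2.160) divided by that ratio. At r = 0.10 this is 1.0085/1.066 = 0.946, or −5%. Break-even is at r of about 0.014.

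**4. Balance missed.** Bias = difference in proportion × 2√r. At 5/8 against 3/8 the difference is 0.25, so r = 0.10 gives 0.25 × 2 × 0.316 = 0.16 residual SD. The standard error of an 8-against-8 contrast is about √(2/8) = 0.5 residual SD.

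**5. Sex added to the plan's power model.** λ = 24 f²/[0.5(1 − r)] with df 2 and 19, solved for 80% power.

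**6. Power for the planned type of test.** This was simulated with three groups, an omnibus gate, Tukey-Kramer, independent errors, the basal covariate taken as already removed, sex balanced and a true whey difference of 1.45 residual SD.

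| r | SE overstated, balanced | CI width change with sex | Bias, 5/8 v 3/8 (SD) | Bias, 6/8 v 2/8 (SD) | Detectable f with sex (stated 0.484) | Power without → with sex |
|---|---|---|---|---|---|---|
| 0 | 0% | +1% | 0 | 0 | 0.486 | about 64%, → about 0.5 points lower |
| 0.05 | 3% | −2% | 0.11 | 0.22 | 0.474 | about 64% → 66% |
| 0.10 | 7% | −5% | 0.16 | 0.32 | 0.461 | about 64% → 69% |
| 0.20 | 14% | −12% | 0.22 | 0.45 | 0.435 | about 64% → 75% |
| 0.30 | 24% | −18% | 0.27 | 0.55 | 0.406 | about 64% → 81% |

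**7. Type I error.** In a plain two-arm test at nominal 5% without sex, simulated size at r = 0.05, 0.10, 0.20 and 0.30 is 4.4%, 3.9%, 3.1% and 2.0% when balanced. At 5/8 against 3/8 it stays near 5%, because the overstated standard error offsets the bias. At 6/8 against 2/8 it is 7% to 14%. With sex in the model it is about 5% and the bias is zero in every case.

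**The case against.** The strongest objection is that no harm is shown. Each subject's own basal measure is already in the model and is assumed to explain half the variation, so it may absorb much of any sex difference. Nothing in the documents shows that a sex effect remains. This stands: every figure is conditional on r. At r = 0 there is no loss and no bias, and at r = 0.05 the standard error is only 3% too large.

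A second objection is that staff will know the Arm 1 counts before Arm 2 opens and already have a stated aim, so gross imbalance is unlikely. This also stands. A numeric target mainly formalises that aim, and dropout in Arm 2 could still upset it. Sex is a recruitment aim here and not a randomisation stratum, so the usual argument for modelling strata does not carry over directly.

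A third objection concerns the test. A two-sample t test puts power at 1.45 SD at about 78% without sex and 81% with it at r = 0.10. The gated Tukey-Kramer analysis gives about 64% and 69%. Its per-contrast size is also lower, about 1.3% without sex and just under 2% with it. The direction and rough gain survive, but the two-sample levels should not be quoted for this trial.

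A reader might infer that the dose comparison in Arm 1 is untouched by the change. Its estimate is, because both doses are taken by the same people. Its standard error is not: with no subject term it uses the pooled residual, so adding sex changes that standard error and the omnibus F.

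**Conclusion.** The point holds as a cheap, conditional improvement. The plan singles out sex as the factor to keep similar between arms and then leaves it out of the model. If sex explains up to 10% of the post-basal variance, the cost is modest: a standard error up to 7% too large when balanced, or a bias of up to 0.16 residual SD at 5/8 against 3/8. It becomes material with a strong residual sex effect (24% and 0.27 SD at 30%) or with gross imbalance (0.22 to 0.55 SD at 6/8 against 2/8 for shares of 5 to 30%).

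A reader might infer that the whey analysis is invalid as planned. The documents do not support that. They give no sex effect. When balance is achieved the test is conservative, and moderate imbalance shifts the point estimate while type I error stays near nominal. Nor would a sex term make the whey contrast equivalent to a randomised one, because arm is not randomised, Arm 2 is enrolled later, and other confounding remains.

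The sizes rest on the assumed range for r and on 8 subjects per arm. The simulated power also rests on independent errors, although Arm 1 subjects contribute two observations each.

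**What to change.** In Section 7.1, prespecify sex as a fixed effect alongside the basal measure in the models for TAR and for FSR (called MPS there).

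Optionally, in Section 3.4, replace the general aim with target numbers of women and men for Arm 2, taken from the Arm 1 counts, which are known when Arm 2 opens.

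The cost is one model term and one sentence. If sex has no effect, the lost degree of freedom costs about 0.5 power points, or about 1% of interval width when balanced. The targets may slightly slow the filling of the last whey places. The plan should also acknowledge that sex adjustment leaves the other differences between sequential, non-randomised arms unaddressed.

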3.5 Blinding

This will be blinded to the extent feasible, given that different beverages will look and taste different. Since the subject has no conscious control over their rate of muscle protein synthesis, total blinding is of no concern. Nonetheless, subjects will not be told which dose of the product they are consuming. The data analyst will need to know the amount and nature of the product being consumed to calculate the rate of protein breakdown.

3.6 Sample Storage

Blood and muscle samples will be kept frozen at -80 degrees Centigrade or colder once the initial processing has taken place. Samples shall be stored in appropriate freezers in the PI's laboratory, located in a restricted area inside the UAMS IOA building. Said freezers are monitored continuously for proper temperature and working condition. With explicit permission via the ICF, all biological samples will be kept indefinitely for future IRB-approved uses. All blood and muscle samples shall be identified using a unique study acronym. None of a subject's personal identifiers shall be present on any biological sample.

4.0 Study Population

Subjects will be recruited using these methods: 1) past subjects that indicated they wanted to be contacted about future studies will be called by study staff to elicit their interest in this study, and 2) the study staff will place IRB-approved flyers around the Little Rock community. Once a potential subject has agreed to come to UAMS for an informed consent discussion, an appointment will be made for them to meet with study staff in the research area of the 3rd floor of the Reynolds Institute at UAMS.

4.1 Inclusion Criteria

- Ages 18-50 yrs.

4.2 Exclusion Criteria

- History of diabetes
- History of malignancy in the 6 months prior to enrollment
- History of gastrointestinal bypass/reduction surgery (Lapband, gastric sleeve, etc.)
- History of chronic inflammatory condition or disease (Lupus, HIV/AIDS, etc.)
- Pregnant females
- Subjects who report regular resistance training exercise > once per week
- Hemoglobin < 9.5 g/dL at the screening visit
- Platelets < 150,000 at the screening visit
- Subjects who cannot safely stop using aspirin for 7 days prior to muscle biopsies
- Concomitant use of corticosteroids (ingestion, injection or transdermal)
- Any other disease or condition that would place the subject at increased risk of harm if they were to participate, at the discretion of the study physician

5.0 Risks and Benefits

There are no direct benefits for the subjects. Expected risks associated with this protocol are described in detail below. All experimental procedures will be performed by appropriately trained and credentialed personnel.

5.1 Blood sampling:

Blood samples will be collected solely for the purpose of experimentation. The blood will be used to determine eligibility and to measure glucose, insulin, plasma amino acid concentrations and stable isotope enrichment. The total amount of blood taken will be approximately 100 mL for subjects in the whey protein isolate arm, and 190 mL for subjects in the EAA/protein arm. Subjects should have no noticeable effects from these volumes.

5.2 DEXA scan:

The DEXA scan exposes subjects to approximately ½ of the radiation of one chest x-ray. They will undergo 1 DEXA scan.

5.3 Muscle samples:

Briefly, the risks related to the biopsy procedure include pain, bleeding, bruising, small scar formation at the biopsy site, Infection, and vaso-vagal response. Muscle biopsies are performed by a physician utilizing local anesthesia (using 1% plain lidocaine) for pain management and strict sterile procedures. Subjects must meet platelet criteria prior to biopsy. See appendices for SOP and related documents.

5.4 Study supplements:

The test composition will be provided by Adesso, LLC. It consists of a proprietary blend of eight essential amino acids and whey protein. It is produced by Prinova, Inc, Carol Stream, IL. This product is not currently commercially available. All components of the composition have been ruled as Generally Regarded as Safe (GRAS) by the FDA. They are natural components of the normal diet. Prinova, Inc, has all necessary certifications for making products for human consumption. Two doses of the product will be tested (approximately 6.3 and 12.6 g of active components). The product comes as powder and will be dissolved in water (8-16 oz) for consumption.

The whey protein isolate is available commercially. The dosage (12.6 g) will be dissolved in water (12 oz). There are no known risks of adverse effects of either the test composition or the whey protein in the dosages used in this study. All components are Generally Regarded as Safe by the FDA, and Prinova Inc has all the necessary certifications for producing and packaging products for human consumption

5.5 Confidentiality:

A potential risk to study participants is the potential for loss of confidentiality. Measures to protect the confidentiality of study participants will be implemented as described in the Data Handling and Record keeping section below.

5.6 Stable Isotope Infusion:

Briefly, the risk related to the isotope infusion is pyrogenic response. All isotope infusions are compounded and prepared by a licensed pharmacist at UAMS. An SOP for infusion procedures will be utilized (see Appendix). All stable isotopes are tested for sterility and pyrogenicity. The stable isotopes will be filtered during infusion through a sterile 0.22 micron (Millipore) filter placed in the infusion line. Stable isotopes are naturally occurring compounds and are not radioactive and are already present in the body in varying amounts. The infusion will be in a 'tracer' dose, i.e., a dose only detectable by GCMS. Infusion of these molecules will increase the level of naturally occurring isotopes by 7-10%. Any adverse reactions during the isotope infusion that suggest infection (urticaria, flushing, nausea, vomiting, sweating, chills, altered heart rate, hypo/hypertension, and hyperthermia) will be promptly addressed by the study physician. Depending on the seriousness of the reaction, the infusion study will be terminated.

6.0 Data Handling and Recordkeeping

Source documents and CRFs will be stored in a secure area of the PI's laboratory. Access will be limited to study personnel. Documents containing identifiers (except the signed ICF) will be destroyed by shredding approximately 7 years after data analysis is completed or publication of data; whichever is longest. The original, signed ICF will be kept indefinitely. At no time shall Protected Health Information be released to non-study personnel.

The Principal Investigator will carefully monitor study procedures to protect the safety of research subjects, the quality of the data and the integrity of the study. All study subject material will be assigned a unique identifying code or number. The key to the code (the instrument associating the data with subject identity) will be kept on a password-protected UAMS server, located behind locked doors in a restricted access area of the UAMS campus. Only those individuals listed on the title page of this protocol and their research staff members will have access to the code and information that identifies the subject in this study. This file will be deleted approximately 7 years after data analysis is completed.

Sponsor (Adesso, LLC) will have monitoring and audit access to source documents and all collected and/or analyzed data. Any data sent to them will remain coded with the unique subject alphanumeric identifier. No identifiable information will leave UAMS.

7.0 Data Analysis

7.1 Statistical Analysis plan

The purpose of this study is to estimate and compare the effect of two different nutritional beverages on total anabolic response (TAR) and muscle protein synthesis (MPS). To this end, an analysis of covariance (ANCOVA) model will be employed to compare the protein sources with respect to mean response (either TAR or MPS) after adjusting for basal measures. If a significant protein group effect is detected, then pairwise comparisons will be performed to determine if the two sources or two doses differ. In this case, the Tukey-Kramer method will be used to adjust for multiple comparisons. A 5% will be used to determine statistical significance.

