2.0 Hypothesis

We propose that consumption of the EAA/protein composition will stimulate the net gain (net protein synthesis) of body protein in a dose-dependent manner. We further propose that the magnitude of increase in net protein synthesis will be greater than induced by the consumption of the same amount of whey protein isolate, which is currently the most popular supplement on the market targeting the stimulation of muscle protein synthesis.

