7.2 Sample Size Calculation & Power Analysis

A total of N=16 subjects will be required for this study, 8 in each arm. With this sample size, the ANCOVA model will have 80% power to detect effect sizes of $f = 0.484$ or larger (Table 1). This estimate assumes the basal covariate explains 50% of the variation in the response and a 5% α -level is used to determine statistical significance.

Table 1. Expected Effect Size by Covariate Variation

Variation Explained by Covariate (%)	Detectable Effect Size, f
10	0.649
30	0.573
50	0.484
70	0.375
90	0.216

(Note that the effect size, f , is simply the ratio of the variation between the three group means and the between-subject variation). In the event the effect of the covariate is mis-specified, the following table presents effect sizes that can be detected as the magnitude of variation explained by the covariate increases from 10% to 90%.

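### The analysis in section 7.1 names no subject or period term for the Arm 1 cross-over; run as Table 1 counts the data, it overstates the dose SE if a subject's two responses are positively correlated

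*Combined protocol and SAP*

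**What the plan says.** The design mixes paired and unpaired data. In section 3.0, "Arm 1 will consist of a group of subjects who will perform a randomized, single blind cross-over (two stable isotope studies"), comparing the two EAA/protein doses. Section 3.2 confirms that "subjects who enrolled into the EAA/protein arm will undergo a second stable isotope study as described above". Arm 2 is made up of different subjects "who will undergo one stable isotope study during which they will ingest the whey protein isolate study supplement". Under section 3.4, the order of the two doses is the only thing randomised.

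Section 7.1 gives one analysis for both TAR and MPS: "an analysis of covariance (ANCOVA) model will be employed to compare the protein sources with respect to mean response (either TAR or MPS"), adjusted for basal measures. If the group effect is significant, "pairwise comparisons will be performed to determine if the two sources or two doses differ", with Tukey-Kramer adjustment at 5%. No subject effect, repeated-measures structure, sequence or period is named. The words two-period in section 3.0 refer to the fasted and post-meal parts of one infusion, not to the cross-over visits.

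Section 7.2 states: "A total of N=16 subjects will be required for this study, 8 in each arm". It claims 80% power at f = 0.484 and says that f "is simply the ratio of the variation between the three group means and the between-subject variation".

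**The concern.** The first hypothesis in section 2.0 is that the product "will stimulate the net gain (net protein synthesis) of body protein in a dose-dependent manner". The cross-over lets each subject serve as their own control for that question. A group-plus-basal ANCOVA with no subject term tests the dose difference against between-subject error and gives up that advantage. A null dose result could then be read as no dose response when the test was conservative. Section 7.2 suggests that the data were in fact counted this way, so its 80% would rest on an independence that 16 subjects do not provide. With the handling of the pairs unstated, the choice could also be made after the data are seen.

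**Working it through.** **Step 1: reproduce Table 1.** Inputs from section 7.2: alpha 0.05, power 80%, three group means, and covariate R² from 10% to 90%. Power comes from the noncentral F with noncentrality λ = N·f²/(1 − R²) and df (k − 1, N − k − 1). For N = 24, k = 3, R² = 0.5 and f = 0.484:

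λ = 24 × 0.484² / 0.5 = 11.24, df 2 and 20, power 0.800.

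Solving for f at 80% power:

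| R² | Printed | N = 24, k = 3 | N = 20, k = 3 | N = 16, k = 3 | N = 16, k = 2 |
|---|---|---|---|---|---|
| 10% | 0.649 | 0.649 | 0.725 | 0.839 | 0.719 |
| 30% | 0.573 | 0.572 | 0.640 | 0.740 | 0.634 |
| 50% | 0.484 | 0.484 | 0.541 | 0.625 | 0.536 |
| 70% | 0.375 | 0.375 | 0.419 | 0.484 | 0.415 |
| 90% | 0.216 | 0.216 | 0.242 | 0.280 | 0.240 |

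All five rows match within 0.001 for 24 independent observations. In the other columns no row matches. With 8 subjects per arm, 24 = 8 + 8 + 8 counts each Arm 1 subject twice.

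**Step 2: SE of the dose contrast.** Take the residual SD after basal adjustment as 1, with 8 observations per dose. Rho is assumed.

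- As counted: √(2/8) = 0.500.
- True: √(2(1 − ρ)/8) = 0.500, 0.418, 0.354 and 0.274 at ρ = 0, 0.3, 0.5 and 0.7.
- Ratio 1/√(1 − ρ): 1.00, 1.20, 1.41 and 1.83.

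Simulating the ANCOVA as counted (20,000 trials per ρ, R² = 0.5) gives slightly smaller ratios, because the residual variance and basal slope are estimated:

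| ρ (assumed) | Model SE | True SE | Ratio | Unadjusted dose rejection under the null, nominal 5% |
|---|---|---|---|---|
| 0 | 0.512 | 0.513 | 1.00 | 5.1% |
| 0.3 | 0.509 | 0.430 | 1.18 | 2.3% |
| 0.5 | 0.506 | 0.364 | 1.39 | 1.0% |
| 0.7 | 0.500 | 0.284 | 1.76 | 0.2% |

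Repeat simulations put the overstatement at about 0%, 17%, 37% and 73%.

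**Step 3: the other contrasts, same four values of ρ.**

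- Family-wise error with the F gate and Tukey-Kramer pairs: 4.4%, 3.7%, 3.5%, 3.4%.
- One dose against whey, unadjusted null rejection: 5.0%, 5.2%, 5.2%, 5.8%.
- Both doses pooled against whey: the as-counted SE is √(1/16 + 1/8) = 0.433, and the true SE is √((1 + ρ)/16 + 1/8) = 0.433, 0.454, 0.468, 0.481. The SE is now too small. Simulated unadjusted null rejection is 5.0%, 6.1%, 7.0%, 8.3%.

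**Step 4: power.** Assume equally spaced means, whey < 6.3 g < 12.6 g, with a step of 0.593 total SD, so f = 0.593 × √(2/3) = 0.484. The basal correlation between visits is assumed to be 0.5. With the F gate and Tukey-Kramer on both sides, dose power is:

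| ρ (assumed) | As counted | Mixed model with subject and visit |
|---|---|---|
| 0 | 22% | 17% |
| 0.3 | 18% | 24% |
| 0.5 | 17% | 33% |
| 0.7 | 13% | 50% |

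Omnibus power at f = 0.484 is 77–79% at ρ = 0, and 73% to 88% at ρ = 0.7 depending on which means differ.

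**The case against.** Section 7.1 is silent on a subject term; it does not exclude one. The paragraph is short, and a power calculation simplified to three groups of eight does not bind the fitted model. This stands, and it is why the conclusion is conditional on analysing the data as counted. Still, no other section supplies the missing structure, and the only model that the plan quantifies treats the visits as independent.

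The size depends on rho, which the documents do not give. At rho 0 there is no SE error and modelling the pairs costs dose power; at 0.3 little is gained. This also stands.

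A reader might infer that repeated subjects must inflate false positives generally. For the three single-pair comparisons the calculations show the opposite: the dose test is conservative and family-wise error stays below 5%. Nor can one say that false positives are never inflated, because section 7.1 does not define its source comparison, and a pooled contrast would be anticonservative.

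A reader might also take the 16-observation calculation (power 0.57 at f = 0.484) as the trial's true power. It is not: 24 observations are planned, some of them correlated, and simulated omnibus power lies on both sides of 80%.

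**Conclusion.** The point holds in conditional form and should be fixed. Two parts are firm: section 7.1 names no subject or period term for a cross-over arm, and Table 1 matches only 24 independent observations. The 24 is inferred from that match; it is not printed.

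The consequence needs two conditions: that the analysis is run as counted, and that rho is positive after basal adjustment. Positive correlation is the usual expectation in a cross-over but is an assumption here. Under both, the dose SE is overstated by about 17% to 73% for rho 0.3 to 0.7, and the unadjusted dose test rejects a true null about 2% to 0.2% of the time. Single-dose contrasts with whey are little affected.

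The stated 80% is omnibus power under independence. It is not badly wrong as an omnibus figure, but it says nothing about the dose contrast, whose power as counted is about 13% to 22% in the one pattern of means examined. Better modelling does not make that contrast well powered: the mixed model reaches 17% to 50%.

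**What to change.** **Section 7.1.** State that all observations are analysed in one model with group (three levels), that visit's basal value, visit (period), and a within-subject covariance or subject effect for Arm 1, using small-sample df such as Kenward-Roger. If a random intercept is used, do not bound its variance at zero: the bounded version gave dose false positives of 6.4–6.6% at rho 0 and 5.3–6.0% at 0.3. A simpler choice for the dose contrast is the within-subject difference adjusted for period and basal difference. Keep Tukey-Kramer. State whether the source comparison is single-dose or pooled. Since whey subjects have only a first isotope visit, also state what the whey contrasts assume about a visit effect.

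**Section 7.2.** State that Table 1 counts 24 observations from 16 subjects as independent, and restate power per contrast over a range of rho that includes 0.

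**Cost.** SAP wording only; data collection is unchanged. Error df for the dose contrast fall from 20 to about 6–7 in the mixed model, or 5 for the simple difference. Dose power therefore drops from about 22% to 17% if rho is near 0, little is gained at 0.3, and the gain is material from about 0.5. With the group-effect gate kept, power for 12.6 g EAA/protein against whey falls from about 75% to 70–73%.

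### Section 7.1 names no subject term for the paired Arm 1 responses, so the standard error of the dose contrast is wrong; the missing visit term is a secondary, conditional matter

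*Combined protocol and SAP*

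**What the plan says.** - **Model (7.1).** An ANCOVA compares the protein sources "with respect to mean response (either TAR or MPS) after adjusting for basal measures". If the overall group test is significant, pairwise comparisons follow with Tukey-Kramer at 5%. No subject, visit, period or sequence term is named, and no mixed or repeated-measures model.
- **Arm 1 (3.0, 3.2).** This is a crossover between the two doses: "subjects who enrolled into the EAA/protein arm will undergo a second stable isotope study as described above", after a washout of at least about a week and using the other leg.
- **Arm 2 (3.0).** "Arm 2 will consist of a group of subjects (with similar gender composition) who will undergo one stable isotope study". Every whey response is therefore from a first infusion. Enrolment is sequential: "After Arm 1 enrollment is completed, unique future subjects will be enrolled into Arm 2".
- **Order (3.4).** "A randomization list will be implemented to reveal which dosage of EAA/protein will be tested first". The section does not say whether the list is balanced.
- **Hypotheses (2.0).** The response is dose-dependent, and the increase "will be greater than induced by the consumption of the same amount of whey protein isolate". Section 5.4 gives the product at about 6.3 and 12.6 g and whey at 12.6 g.
- **Sample size (7.2).** 16 subjects, 8 per arm, with 80% power for f = 0.484 when the basal covariate explains 50% of the variation.

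**The concern.** Two responses from one person are normally correlated. A model without a subject term prices the dose comparison as if it came from two separate groups of eight. The point estimate is unaffected, but its standard error, confidence interval and test are not those of a crossover. The dose comparison bears on the first hypothesis in section 2.0 and is the only randomised comparison in the study.

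The second strand concerns whey. Randomising dose order balances first and second infusions between the two doses only. Whey has no second infusion, so a residual visit effect would push both doses the same way relative to whey.

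**Working it through.** **Reproducing Table 1.** For a three-group ANCOVA with one covariate, the noncentrality is N·f²/(1−R²) with 2 and N−4 df. With N = 24 infusions, f = 0.484 and R² = 0.5, it is 24 × 0.2343 / 0.5 = 11.24 on 2 and 20 df, and power is 0.800. All five rows give power of 0.799 to 0.801. With 16 observations and R² = 50%, the detectable f would be 0.625 (three groups) or 0.536 (two groups). The sizing therefore treats 24 infusions as independent, which agrees with a model that has no subject term.

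**Dose contrast.** Let one basal-adjusted response have SD 1, and let ρ be the correlation between a subject's two adjusted responses. The documents give no ρ, so the values are assumptions.

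- Model SE, pairing ignored: √(1/8 + 1/8) = 0.50.
- True SE: √(2(1−ρ)/8).

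| ρ | True SE | Model SE / true SE | Null rejection, unadjusted 5% test (simulated) |
|---|---|---|---|
| 0.3 | 0.42 | 1.20 | about 2.4% |
| 0.5 | 0.35 | 1.41 | about 0.9% |
| 0.7 | 0.27 | 1.83 | about 0.1% |

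Pairing has a price in df. With eight pairs and a basal slope, about 8 − 2 = 6 df remain (t = 2.447), against 20 in the plain model (t = 2.086). The unadjusted 95% half-width is 2.086 × 0.50 = 1.04 SD in the plain model. In the paired model it is 2.447 × 0.418 = 1.02, 2.447 × 0.354 = 0.87 and 2.447 × 0.274 = 0.67 SD. The gain is negligible at ρ = 0.3 and clear at 0.5 and 0.7.

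**Dose minus whey.** The subjects differ, so the true SE is √(1/8 + 1/8) = 0.50, as the plain model states. The missing subject term does little harm here.

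**Visit effect.** Let π be the second-minus-first effect left after adjustment for the same-day basal value. If all Arm 1 subjects complete both infusions, the bias of a dose minus whey is π times that dose's share of second infusions:

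- 4/4 split: 4/8 = 0.5π for each dose, and 0 for the dose contrast.
- 6/2 split: 6/8 = 0.75π and 2/8 = 0.25π, and 0.75π − 0.25π = 0.5π for the dose contrast.

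Simulated false-positive rates under the planned procedure (significant overall test, then Tukey-Kramer), with no true difference, no visit term and ρ from 0.3 to 0.7:

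| Assumed π (SD) | 12.6 g vs whey, 4/4 | Either dose vs whey, 4/4 |
|---|---|---|
| 0.25 | about 2% | about 3.6% |
| 0.5 | about 3% | about 4.7% |
| 1.0 | about 5% | about 8% |

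At 6/2 with 12.6 g mostly second and π = 1.0 SD, the rate for 12.6 g versus whey is about 13%.

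**Price of a visit term at 4/4.** The visit effect is estimated from Arm 1 with variance v = 2(1−ρ)/8, which is 0.175, 0.125 and 0.075 at ρ = 0.3, 0.5 and 0.7. The SE of one dose minus whey becomes √(0.25 + 0.25v) = 0.542, 0.530 and 0.518, a rise of 8%, 6% and 4%. Mean squared error is 0.25 + 0.25v with the term and 0.25 + 0.25π² without it. The term helps only when π exceeds √v = 0.42, 0.35 and 0.27 SD.

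**The case against.** **On pairing.** Section 7.1 is brief and does not forbid a subject effect, and Table 1 is a sizing calculation rather than an analysis commitment. With positive correlation the error is conservative, so no false claim of a dose difference follows. If basal adjustment removes most of the between-subject correlation, little precision is lost. All of this is fair, and it limits the size of the point. It does not make the stated model right for paired data.

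**On visit.** The documents give no evidence that π differs from zero. Each infusion has its own basal period, there is a washout, and the infusion procedure is standardised. A visit term rests on eight subjects and raises mean squared error if π is small. A 6/2 split with 12.6 g mostly second would occur with probability 28/256, about 11%, even under simple randomisation, and silence on blocking does not show that the list is unbalanced. These objections stand, and they are why the visit term comes second.

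**Stronger readings that the documents do not support.**

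- A reader might infer that the whey comparisons are biased by visit. They would be only if a residual visit effect exists, and nothing shows one.
- A reader might infer false-positive rates of about 6%, 7% and 12% for π of 0.25, 0.5 and 1.0 SD at 4/4. Those belong to a single unadjusted comparison, not to the procedure in 7.1.
- A reader might blame the missing subject term for bias. It alters standard errors, not estimates.

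**Conclusion.** The concern holds in this form and is minor. As written, 7.1 overstates the standard error of the dose contrast by a factor of 1.20 to 1.83 for ρ between 0.3 and 0.7. That range is assumed, and the practical gain from correcting the model depends on ρ being more than about 0.3.

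The visit bias is conditional. At a 4/4 split the planned procedure keeps the chance of declaring either dose different from whey below 5% up to π = 0.5 SD, and exceeds it (about 8%) at 1.0 SD. A lopsided order list would make matters worse. The later, non-randomised enrolment of Arm 2 is a larger threat to the whey comparisons, and neither a subject nor a visit term corrects it.

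**What to change.** 1. In 7.1, fit TAR and MPS with mixed models containing basal measure, protein group (three levels) and a random subject effect. The effect must be random: with fixed subject effects the whey contrasts cannot be estimated. State the df method, and apply Tukey-Kramer with each contrast's own standard error.
2. In 3.4, generate the Arm 1 order list in blocks so that four of eight subjects start with each dose. This sets the visit bias of the dose contrast to zero when all complete, and avoids the 6/2 case.
3. Add a fixed visit effect (first versus second infusion; all whey responses are first), in the main model or as a prespecified sensitivity analysis. State that it assumes an equal visit effect for both doses and no carryover, and that it does not address how Arm 2 is enrolled.

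The cost is a sentence or two in 7.1 and one line in 3.4, with no extra subjects or samples. The subject effect leaves fewer df for the dose contrast. The visit term raises the SE of one dose versus whey by about 4-8% at 4/4, takes one further df, and lowers mean squared error only above about 0.27-0.42 SD.
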